1.1.2 Secondary objectives

Additional objectives are to test the feasibility of conducting a confirmatory RCT to prevent IAD and to evaluate the feasibility of measuring the Core Outcome Domains for IAD trials.

The trial will answer the following research questions:

- What are the effect sizes of the outcomes when comparing the intervention groups and the control group?
- Is the implementation of a standardized skin protection regime for the prevention of IAD feasible in geriatric hospital wards and nursing homes?
- Does the implementation of a standardized skin protection regime for the prevention of IAD reduce IAD-related itch and IAD-related pain?
- Is the measurement of Core Outcome Domains for IAD trials feasible?

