current condition		skin_0062		1-Homogeneous redness with scattered papules 2- Homogeneous redness and homogeneous infiltration 3- Homogeneous redness and infiltration with vesicles 4- Homogeneous redness and infiltration with coalescing vesicles	n (%)

Functional assessments					
Characteristic	eCRF table	Variable name	Type	Scale	Comment/Analysis
MMSE	mnppid_assessments (day0) mnppid_assessments1 (else)				Relevant for dementia and IAD related pain
MMSE-Score	mnppid_assessments	Func_0021	Numeric	Score; Range 0-30	Mean (sd)

Functional assessments					
Characteristic	eCRF table	Variable name	Type	Scale	Comment/Analysis
MMSE Score unknown	mnppid_assessments	Func_0022	cat	0-no 1-yes	
Has the subject a MMSE Score of 24 or higher?	mnppid_assessments1	Func_0090			Check func_0021
Cognitive Ability	mnppid_assessments	Func_0030		1-≥ 24 (Normal cognition; no dementia) 2-19 to 23 (Mild dementia) 3-10 to 18 (Moderate dementia) 4-9 and lower (Severe dementia)	N (%) Result of func_0021
Barthel Index Physical function	mnppid_assessments	Func_0041	Numeric	Score; Range 0-100	Mean (sd)
Barthel Index unknown	mnppid_assessments (day0)	Func_0042	cat	0-no 1-yes	
IAD related pain					Choice of Score depending on MMSE
IAD present?	mnppid_assessments (day0)	func_0057	cat	0-no 1-yes	Compare with skin_0011
NRS (numeric rating scale)	mnppid_assessments (day0) mnppid_assessments1 (else)	Func_0052 (day0) func_0101	Numeric	0 - 10 [numeric]	Mean (sd) if (MMSE Score ≥ 24) (check func_0051) (check func_0102 and 0103)
PAINAD-G	mnppid_assessments (day0) mnppid_assessments1 (else)	Func_0054 (day0) func_0111	Numeric	0 - 10 [numeric]	Mean (sd) if (MMSE Score < 24) (check func_0053) (check func_0112 and 0113)
No assessment	mnppid_assessments (day0)	Func_0055	cat	0-no 1-yes	
IAD related itch					
IAD-related itch reported by patient?	mnppid_assessments (day0) mnppid_assessments1 (else)	Func_0061 (day0) func_0121	cat	-2-No assessment -1- N.A. (no IAD present) 0-No 1-Yes	Func_0062 and func_0122 for missing analysis

Functional assessments					
Characteristic	eCRF table	Variable name	Type	Scale	Comment/Analysis
Patient satisfaction (of incontinence treatment)	mnppid_assessments (day0) mnppid_assessments1 (else)	Func_0071 (day0) func_0131	Numeric	0 - 10 [numeric]	Mean (sd) if (MMSE Score \geq 24) (check func_0053) NRS from 0 (= dissatisfied) to 10 (= very satisfied) (check func_0072 for missings) and func_0132,func_0133)

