4.4 Efficacy

The main efficacy variable is the IAD cumulative incidence measured by IAD presence on each visit day (Day0, Day2, ..., Day14). Secondary efficacy variables are Erythema and Maceration level, IAD itch and pain level and patient satisfaction.

- IAD-related itch and pain level (numeric rating scale) are measured at each visit day (Day0, Day2, ..., Day14) if IAD is present and if MMSE \geq 24.
- IAD itch and pain level (PAINAD-G) are measured at each visit day (Day0, Day2, ..., Day14) if IAD is present and if MMSE < 24.
- Patient satisfaction is measured at each visit day (Day0, Day2, ..., Day14) if MMSE \geq 24
- Erythema and Maceration level are measured at each visit day (Day0, Day2, ..., Day14).

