5.1 Missing values

In all analyses, missing values on either the outcome measures or on the covariates will be handled by using multiple imputation by chained equation (MICE) with $m = 30$ imputed datasets if MAR or MCAR assumption holds. To evaluate whether individual missings are MAR, MCAR or MNAR we will use information on reasons of missings or drop out (e.g. if patients drop out due to worsening of health status or not). In case of death, no imputation will be implemented for the time afterwards.

6 Sample size

Due to the exploratory nature of the trial, a formal sample size calculation is not applicable [23]. The trial has two subgroup strata (I) sex (male/female); (II) condition of the skin (no IAD vs. IAD Category 1A) and three treatment arms. Based on these conditions and following the recommendations for exploratory trials [36], a sample size of $n = 60$ participants per treatment group is considered feasible and sufficient to describe group differences. In order to compensate a possible loss-to-follow-up, $n = 70$ patients per group will be included.

7 Statistical analyses / methods

For all analyses, appropriate descriptive statistics (mean, standard deviation, median, interquartile range, absolute and relative frequencies) depending on the scale and distribution of the outcome variable for each time point will be presented. For relative frequencies of outcome variables, their cumulative incidences will be reported as well. Sensitivity analyses include per protocol analyses and complete case analyses in the ITT (without imputation).

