7.2 Analyses of endpoints

Because of the exploratory nature of the trial and according to methodological guidance for exploratory trials, a distinction between primary and secondary endpoints is not made [23]. Because the main aim is to prevent IAD, IAD incidence is likely to be considered as a primary outcome in a possible subsequent confirmatory trial and is therefore considered as primary efficacy variable.

For all outcomes, total group differences are reported by the corresponding effect size based on the statistical models as outlines below and corresponding 95% confidence intervals. Relevant timepoints will be Day 6 and Day14. Day0 reports will be presented as is.

The relevant blinded group comparisons are: A vs. B; A vs. C; B vs. C.

For cumulative incidence rates of IAD, Kaplan-Meier Curves will be presented with time ranging from inclusion to IAD onset, i.e. the first occurrence of IAD 2A or 2B. Censoring occurs if patients withdraw from the study before the onset of an IAD or if the study is terminated before IAD onset. Mixed effects Cox regression model (shared frailty model) will be carried out for group comparisons of incidence rates. The latter includes group allocation, sex, setting (nursery home, geriatric hospital ward) and time (continuous) as fixed effects and random intercepts for the ward and the patients. The resulting Hazard ratios for IAD will be presented. Potential non-linear time effects will be explored and modelled using fractional polynomials or splines.

Group differences for categorical, dichotomous responses are calculated by estimating group effects from either generalized linear mixed-effects models (binary logistic) - including particular baseline status (maceration, IAD-related itch), group allocation, sex, setting and time as fixed effects and random intercepts per ward and patients - or nonparametric analysis of longitudinal data depending on the distribution of the data. For the Erosion model, no baseline adjustment is considered due to its presence is an exclusion criterion.

List:

- Erosion (no/ yes)
- Maceration (no/ yes)
- IAD related itch (no/ yes) [only measured if IAD present]
- IAD-related pain (no/yes) [only measured if IAD present]

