Group differences for numerical, ordinal responses are calculated by estimating group effects from either cumulative link mixed-effects (ordinal) - adjusted for baseline status, group allocation, sex, setting and time as fixed effects and random intercept per ward-ID and patient as random effects - or nonparametric analysis of longitudinal data depending on the distribution of the data.

In case of non-occurrence of one category, the model will reduce to a generalized linear mixed-effects models (binary logistic) as stated above.

List:

- Erythema (none/pink/red or bright red)

Group differences for numeric, interval scaled responses are calculated by estimating group effects from either linear mixed-effects models - adjusted for baseline status, group allocation, sex, setting and time as fixed effects and random intercept per ward and patient as random effects - or nonparametric analysis of longitudinal data depending on the distribution of the data.

List:

- Erythema (total) level (in arbitrary units (AU) from 0 to 999)
- IAD related pain (numeric rating scale from 0 to 10) [for IAD present]
- Patient satisfaction (numeric rating scale from 0 to 10) [both: for MMSE ≥ 24 and above]

In case of nonlinear relationship, nonlinear mixed-effects models will be considered. The check will occur visually by scatterplots.

The distribution of outcome variables will be checked by raincloud plots (boxplot + histogram).

No adjustment for multiple comparisons will be made and results are bound to be seen exploratory.

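### Itch and pain are compared between arms only at visits with IAD present, so the contrast is not a randomised comparison and does not answer the stated question on itch and pain

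*Combined protocol and SAP*

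**What the plan says.** SAP 7.2 lists the outcomes for each model type and attaches a condition to three of them:

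- itch, binary logistic mixed model: "IAD related itch (no/ yes) [only measured if IAD present"
- pain as a binary outcome, same model: "IAD-related pain (no/yes) [only measured if IAD present"
- pain score, linear mixed model: "IAD related pain (numeric rating scale from 0 to 10) [for IAD present"

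SAP 4.4 makes this a rule for measurement at every visit. For participants with MMSE below 24, "IAD itch and pain level (PAINAD-G) are measured at each visit day (Day0, Day2, ..., Day14) if IAD is present"; the parallel rule for MMSE of 24 or higher uses the numeric rating scale. In the SAP 4.2 table, the itch item has a separate code for visits without IAD, with the label "1- N.A. (no IAD present" (the code is minus one). It is distinct from 0 (no itch) and from minus two (no assessment).

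The itch model includes baseline itch as a fixed effect, and the pain-score model adjusts for baseline status. SAP 5.1 states: "In all analyses, missing values on either the outcome measures or on the covariates will be handled by using multiple imputation", provided the data are MAR or MCAR. It does not mention the not-applicable code.

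The research question in SAP 1.1.2 is: "Does the implementation of a standardized skin protection regime for the prevention of IAD reduce IAD-related itch and IAD-related pain". It is not limited to people who have IAD. Protocol 2.7.3 and Table 3 schedule itch and pain at each visit without an IAD condition.

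**The concern.** Under SAP 4.2 and 7.2, IAD presence is the main outcome, and preventing it is the purpose of both products. If a product works, the arm helps to decide which visits enter the itch and pain comparison. Randomisation no longer protects that comparison. The restriction also removes one route by which a preventive regime can reduce these symptoms, namely that fewer people get IAD at all.

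The baseline covariate adds a second problem. Everyone free of IAD at Day 0 has the not-applicable code for baseline itch, and this group supplies all the new IAD cases. The SAP does not say how the code enters the model or the imputation, so two analysts could follow the plan and obtain different results.

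What is at stake is one of four research questions, and effect sizes with confidence intervals that may inform the design of a confirmatory trial.

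**Working it through.** The documents give no rate, effect size or power figure for itch or pain, so there is no figure to reproduce. The check compares two quantities per arm:

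- all randomised: P(itch) = P(mild IAD) × P(itch | mild) + P(severe IAD) × P(itch | severe), with no IAD counted as no IAD-related itch
- planned contrast: P(itch | IAD) = P(itch) / P(IAD)

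**Illustration 1 (all rates assumed).** Control has 30% mild and 10% severe IAD; protectant has 12% and 8%. Itch occurs in 30% of mild and 70% of severe cases.

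- All randomised, control: 0.30 × 0.3 + 0.10 × 0.7 = 0.160
- All randomised, protectant: 0.12 × 0.3 + 0.08 × 0.7 = 0.092
- OR = (0.092/0.908) / (0.160/0.840) = 0.53
- IAD only: control 0.160/0.40 = 0.40; protectant 0.092/0.20 = 0.46
- OR = (0.46/0.54) / (0.40/0.60) = 1.28

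**Illustration 2.** Control IAD presence is set to 35.4%, the long-term-care prevalence in protocol 1.1, used here as an assumption. Also assumed: 75% of control IAD is mild, with itch in 20% of mild and 60% of severe cases. Itch among control cases is then 0.75 × 0.2 + 0.25 × 0.6 = 30%, and in all control participants 0.354 × 0.30 = 10.6%.

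| Assumed product effect | Itch, all randomised (control vs product) | OR, all randomised | Itch, IAD only | OR, IAD only |
|---|---|---|---|---|
| none | 10.6% vs 10.6% | 1.00 | 30% vs 30% | 1.00 |
| halves all IAD | 10.6% vs 5.3% | 0.47 | 30% vs 30% | 1.00 |
| prevents half of mild IAD only | 10.6% vs 8.0% | 0.73 | 30% vs 36% | 1.31 |
| prevents half of severe IAD only | 10.6% vs 8.0% | 0.73 | 30% vs 25.7% | 0.81 |

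The IAD-only ORs do not depend on the control IAD level. At 15% and 40% they are the same, while the all-randomised ORs move only to 0.49 and 0.47 (halves all IAD) and to 0.74 and 0.73 (mild only or severe only).

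**Size of the compared sets.** With the planned 60 analysed per arm and 35.4% IAD, halving IAD leaves about 60 × 0.354 = 21 control and 60 × 0.177 = 11 product participants at a given visit.

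**Sensitivity analyses.** SAP 7 plans per-protocol and complete-case analyses. Neither lifts the IAD condition.

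**The case against.** The strongest reply is that the contrast among affected people is a coherent question about symptom severity, that the outcomes are secondary, and that SAP 7.2 disclaims confirmatory tests. Precision is also low. With the rates of illustration 1 and 60 per arm (24 vs 12 with IAD, one visit, no clustering), the standard error of log OR 1.28 is √(1/(24×0.40×0.60) + 1/(12×0.46×0.54)) = 0.71, giving a 95% CI of about 0.32 to 5.2. For the all-randomised OR of 0.53 it is √(1/(60×0.160×0.840) + 1/(60×0.092×0.908)) = 0.57, giving about 0.17 to 1.6. Neither would be read as firm harm or benefit. This stands and limits the severity. It does not make the contrast an answer to the question in SAP 1.1.2.

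SAP 7 also calls for absolute frequencies at each time point, so a reader could divide itch counts by arm size. That helps only in part: the denominator of assessable participants is not defined, and no effect size or interval would follow.

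Two stronger readings are tempting. A reader might infer that the planned result is bound to be biased, or will make a good product look harmful. The documents do not support this. The reversal needs a product that prevents mainly mild IAD, and nothing in the plan suggests that pattern. If mainly severe IAD is prevented, the direction is preserved. Category 1A is also allowed at Day 0, so some of the IAD-positive group had IAD before randomisation, although its presence at Days 2 to 14 is still post-randomisation.

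A reader might also infer that MICE will create symptoms in participants with healthy skin. SAP 5.1 imputes missing values and never says that not applicable counts as missing, and SAP 4.2 keeps the two codes apart. Nor is dropping these participants the only alternative, since the code could be kept as its own baseline level. What stands is that the SAP leaves this open.

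**Conclusion.** The concern holds in a limited form. The itch and pain contrasts in SAP 7.2 condition on a post-randomisation outcome that the products target. They are not randomised comparisons, and they omit the benefit that comes from preventing IAD. They therefore do not answer the SAP 1.1.2 question, whichever way the data fall.

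How far they depart from the all-randomised effect is unknown. Under the assumed rates the planned OR ranges from 0.81 to 1.31 where the all-randomised OR is between 0.47 and 0.73. The two agree at 1.00 if the products affect neither IAD presence nor severity mix. The handling of the not-applicable code, as baseline covariate and in the imputation, is unspecified rather than wrong. This should be fixed; it does not threaten the main IAD analysis.

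**What to change.** - Make the between-arm analysis of IAD-related itch (yes/no) and pain (yes/no, or ordinal) an analysis of the full analysis set among participants assessable for the item. Say how a pain category is derived from the two 0–10 scales.
- Define assessable by the Day 0 MMSE. First reconcile protocol 4.1.3, which gives the itch and pain questionnaires only to those scoring 24 or higher, with SAP 4.4, which also lists itch below 24.
- Count not applicable because of no IAD as no itch and no pain at every visit, including Day 0. State that this value is structural and is not imputed. The SAP 4.2 table shows the code for itch only, so for pain it must be derived from the IAD rating where no score was recorded.
- Treat no assessment, and visits with missing IAD status, as missing under SAP 5.1.
- Itch and pain are collected by the unblinded team member and IAD is rated by the blinded one, so the two can disagree. Where a symptom was recorded but the blinded rating shows no IAD, keep the recorded value and resolve it by a stated rule or a sensitivity analysis.
- Report IAD-only results as descriptive, labelled as a non-randomised comparison.

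The cost is SAP wording, a recode of existing variables and a rule for discordant records; no new data are needed. The drawback is many zeros: the outcome will largely track IAD presence, and the 0–10 pain score becomes less suited to a linear model.

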2.7.3 RESIDENT/PATIENT REPORTED OUTCOME MEASURES

Participants are asked if IAD related itch is present or not. IAD related pain will be assessed with a numeric rating scale (NRS) from 0 (= no pain) to 10 (= worst possible pain) (**Fehler! Verweisquelle konnte nicht gefunden werden.**) for patients/residents without cognitive impairment (according to Mini-Mental-State-Examination (MMSE) [29] (**Fehler! Verweisquelle konnte nicht gefunden werden.**) with scores of 24 or higher). For patients/residents with dementia (according to MMSE [29] scores of < 24) the Pain Assessment in Advanced Dementia (PAINAD-G) [30, 31] scale will be used (**Fehler! Verweisquelle konnte nicht gefunden werden.**). Patient satisfaction is assessed by

NRS from 0 (= dissatisfied) to 10 (= very satisfied) (**Fehler! Verweisquelle konnte nicht gefunden werden.**) for patients/residents with MMSE [29] scores of 24 or higher. Definition according to [32].

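### IAD-related itch and pain are compared only at visits with IAD, an outcome the products are meant to prevent, so the contrast is not between randomised groups

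*Combined protocol and SAP*

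**What the plan says.** SAP 1.1.2 asks: "Does the implementation of a standardized skin protection regime for the prevention of IAD reduce IAD-related itch and IAD-related pain". The question is about the regime and is not limited to people who still have IAD.

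Protocol 2.7.3 sets no IAD condition on itch ("Participants are asked if IAD related itch is present or not"), and protocol Tables 2 and 3 schedule itch and pain at all eight visits.

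The SAP adds a condition. In section 4.4, "IAD-related itch and pain level (numeric rating scale) are measured at each visit day (Day0, Day2, ..., Day14) if IAD is present", and the bullet for participants with MMSE below 24 repeats it. Section 7.2 then lists three outcomes for modelling:
- itch: "IAD related itch (no/ yes) [only measured if IAD present"
- binary pain: "IAD-related pain (no/yes) [only measured if IAD present"
- the pain score: "IAD related pain (numeric rating scale from 0 to 10) [for IAD present"

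The eCRF coding in SAP 4.2 follows the same logic. Itch at a visit without IAD has its own code, -1, separate from 0 for no itch: "N.A. (no IAD present) 0-No 1-Yes". A further code, -2, marks no assessment.

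SAP 4.2 names presence of IAD at the visit (skin_0011) as the main outcome variable. No SAP text counts an IAD-free visit as symptom-free, declares an effect among IAD cases to be the intended target, or deals with the selection.

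**The concern.** The visits entering the itch and pain models are chosen by a variable that treatment can change. Each arm contributes only the IAD visits it still has, so a product that prevents IAD removes its own successes from the comparison. The visits left in two arms may differ in severity and in the people who supply them, even though the arms were balanced at randomisation. SAP 2.2 gives preserving the randomisation as the purpose of the ITT analysis; this restriction works against it.

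At stake is a named research question. The trial's purpose is to supply effect sizes for a possible confirmatory trial. An effect size for symptoms given IAD is a different quantity from the effect on symptoms in everyone allocated, and a larger sample does not bring the two together.

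**Working it through.** **No figure to reproduce.** The documents state no itch rate, pain rate or expected effect, so all rates below are assumptions chosen to show how the two contrasts relate.

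**Illustration.** Assume that control has mild IAD at 20% of visits and severe IAD at 10%, with itch at 25% of mild and 70% of severe IAD visits. With m and s the shares of visits with mild and severe IAD:
- itch over all visits B = 0.25m + 0.70s
- itch given IAD q = B/(m + s)
- crude OR among IAD visits = [q₁/(1 − q₁)] / [q₀/(1 − q₀)]; the all-visit OR uses B in place of q

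Control: B = 0.05 + 0.07 = 0.12; q = 0.12/0.30 = 0.40.

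| Share prevented (mild / severe) | m, s | B | Ratio of B to control | q | OR, IAD visits | OR, all visits |
|---|---|---|---|---|---|---|
| (a) 50% / 50% | 0.10, 0.05 | 0.060 | 0.50 | 0.060/0.15 = 0.400 | 1.00 | 0.47 |
| (b) 60% / 20% | 0.08, 0.08 | 0.076 | 0.63 | 0.076/0.16 = 0.475 | 1.36 | 0.60 |
| (c) 80% / 20% | 0.04, 0.08 | 0.066 | 0.55 | 0.066/0.12 = 0.550 | 1.83 | 0.52 |
| (d) 20% / 60% | 0.16, 0.04 | 0.068 | 0.57 | 0.068/0.20 = 0.340 | 0.77 | 0.54 |

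Example, row (b): (0.475/0.525)/(0.40/0.60) = 1.36 among IAD visits, and (0.076/0.924)/(0.12/0.88) = 0.60 over all visits.

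Itch falls in every row. The IAD-visit contrast reads as no effect in (a), harm in (b) and (c), and a diluted benefit in (d).

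**Second set of inputs.** Take the 35.4% background prevalence in protocol 1.1 as the control rate per visit (an assumption).
- IAD halved, itch given IAD 40% in both arms: all-participant itch goes from 0.354 × 0.40 = 14.2% to 0.177 × 0.40 = 7.1%, while the IAD-visit OR is 1.00. With 60 per arm, that OR rests on about 21 against 11 participants with IAD (60 × 0.354 and 60 × 0.177). It stays at 1.00 for control IAD rates from 15% to 40%.
- Half the IAD mild, itch 20% in mild and 60% in severe IAD, half the mild IAD prevented: 40.0% against 46.7% among IAD visits, OR 1.31; over all participants 14.2% against 12.4%, OR 0.86.
- If mild and severe IAD itch equally, preventing mild IAD gives an IAD-visit OR of 1.00, not harm.

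**Does baseline adjustment remove it?** A simulation with 20,000 per arm and seven follow-up visits used a logistic GEE adjusted for time, baseline itch and baseline IAD:
- IAD slightly more than halved: adjusted OR 0.97 among IAD visits against 0.38 over all visits
- half of mild IAD prevented: 1.27 against 0.83
- severity lowered throughout, with itch rising with severity: 0.82 against 0.33

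Adjustment does not remove the gap.

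**The case against.** **Direction.** A reader might infer that the planned analysis will hide a benefit or show harm. The documents do not support that. No effect requires equal itch given IAD in the arms; apparent harm requires that the IAD prevented is mainly mild and itches less than severe IAD. No symptom rates by GLOBIAD category are given, and row (d) points the right way.

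**Model.** SAP 7.2 plans mixed models with ward and patient intercepts, or a nonparametric alternative. The figures above are crude or GEE odds ratios, so they show the mechanism and do not predict the reported estimate. This stands.

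**Collection or analysis.** For itch and binary pain, the bracket in 7.2 strictly describes when data were collected; only the pain-score entry reads as an analysis condition. Restriction of the models is still the natural reading, because no rule gives IAD-free visits a value.

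**Imputation.** It is tempting to add that multiple imputation under SAP 5.1 will fill IAD-free visits with symptoms that cannot exist. That is only a possibility: the eCRF separates not applicable (-1) from not assessed (-2), and 5.1 nowhere says that -1 is missing. A clarifying sentence is enough.

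**Importance.** Itch and pain are secondary, nothing is confirmatory, and prevention of IAD has its own time-to-event analysis, so that benefit is not lost from the report. SAP section 7 also promises cumulative incidences, but without a denominator, so they mitigate only in part. Precision would remain low: for 14.2% against 7.1% with 60 per arm at one visit, power is about 24% (0.0708/0.0559 = 1.27 standard errors). The change corrects what is estimated, not how precisely. These points lower the severity; they do not make the contrast answer the question.

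**Conclusion.** The concern holds. As written, the itch and pain contrasts are conditional on a post-randomisation outcome that the products are meant to prevent. They are not comparisons of the randomised groups and do not answer the question in SAP 1.1.2. This follows from the text and needs no assumed rate.

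The size and direction of the distortion do rest on assumed rates. In the illustration, the crude OR among IAD visits is 1.00 when itch over all visits halves, 1.36 to 1.83 when itch falls by 37% to 45%, and 0.77 when it falls by 43%. The supportable statement is that the contrast can show no effect, harm, or a benefit of the wrong size.

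Severity is moderate, because the outcomes are secondary and the trial is exploratory. The main IAD analysis is not touched by this point.

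**What to change.** In SAP 4.4, 5.1 and 7.2:

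1. Make the main itch and pain contrast an analysis of all attended visits of all full-analysis-set participants to whom the instrument applies.
2. Where the blinded assessor records skin_0011 = 0 and itch is coded -1, or pain was not assessed because there was no IAD, set itch to no and pain to 0. Exclude these visits from imputation.
3. Where skin_0011 = 1 and itch is coded -1 or as not assessed, treat the value as missing.
4. Where a recorded symptom conflicts with skin_0011, raise a query; do not overwrite it.
5. Reconcile protocol 4.1.3, which limits the itch questionnaire to MMSE of 24 or higher, with SAP 4.4, which also lists itch for MMSE below 24, so that the itch population is defined.
6. Analyse pain as any pain yes/no or with an ordinal model, because the score will contain many zeros.
7. Report symptoms among visits with IAD descriptively, labelled as not a randomised comparison.

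The cost is SAP wording and one recode; no new data are needed. The downsides are a zero-heavy pain score and an endpoint that partly overlaps IAD occurrence, which the report should say.

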4.2 Outcome variables

Because of the exploratory nature of the trial and according to methodological guidance for exploratory trials, a distinction between primary and secondary endpoints is not made [23]. The presence of IAD is, however, with consideration of the study protocol considered as main outcome variable, i.e. primary outcome.

Variables marked with (day0) will be considered as baseline data. All outcome variables are measured in eight study visits in total (one baseline visit [Day0] and seven follow-up visits [Day2, Day4, ..., Day14]).

Characteristic	eCRF table	Variable name	Type	Scale	Comment/Analysis
IAD incidence	mnppid_skin				Main outcome Measured via occurrence of IAD at given visit (skin_0011)
IAD present?		skin_0011	cat	0-no 1-yes	n (%)
Location front		skin_0015	cat	0-no 1-yes	n (%)
Location back		skin_0016	cat	0-no 1-yes	n (%)
GLOBIAD category (front)		skin_0012	cat	1-1A 2-1B 3-2A 4-2B	n (%) (check skin_0015)
GLOBIAD category (back)		skin_0017	cat	1-1A 2-1B 3-2A 4-2B	n (%) (check skin_0016)
Erythema (visual)					Multi variable
"Redness?"		skin_0021		0-None 1-Pink 2-Red/bright red	main focus if available, else build variable based on 0026, 0027a and 0028a; (highest level counts) n (%)
n.a.		skin_0023		0-no 1-yes	Check if contradicts skin_0026, 0027a and 0028a
None		skin_0026		0-no 1-yes	
Pink		skin_0027a		0-no 1-yes	
Front		skin_0027b		0-no 1-yes	n (%)
Back		skin_0027c		0-no 1-yes	n (%)
Red/bright red		skin_0028a		0-no 1-yes	
Front		skin_0028b		0-no 1-yes	n (%)
Back		skin_0028c		0-no 1-yes	n (%)
Erythema level (1)		Func_0081 (day0) func_0141	Numeric	Arbitrary units (AU) from 0 (= no erythema) to 999 (= extreme erythema)	Mean (sd) check func_0082 func_0142, func_0143
Erythema level (2)		Func_0083 (day0) func_0144	Numeric	Arbitrary units (AU) from 0 (= no erythema) to 999 (= extreme erythema)	Mean (sd) check func_0084

Characteristic	eCRF table	Variable name	Type	Scale	Comment/Analysis
					func_0145, func_0146
Erythema level (total)			Numeric	Arbitrary units (AU) from 0 (= no erythema) to 999 (= extreme erythema)	Mean (sd) of (Erythema level 1 + Erythema level 2)/2
Erosion					
"Erosion present?"		skin_0041		0-no 1-yes	n (%)
Front		skin_0044		0-no 1-yes	n (%)
Back		skin_0045		0-no 1-yes	n (%)
Maceration					
"Maceration present?"		skin_0051		0-no 1-yes	n (%)
Front		skin_0054		0-no 1-yes	n (%)
Back		skin_0055		0-no 1-yes	n (%)
Local intolerances					
Have any local intolerances occurred since the last visit?		skin_0061		0-no 1-yes	n (%)

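### SAP 7.2 names Day 6 and Day 14 as the timepoints of interest, but its longitudinal models have no group-by-time term to produce them, and adding one while keeping only random intercepts would make the linear model's Day 14 interval too narrow

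*Combined protocol and SAP*

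**What the plan says.** SAP 4.2 schedules "one baseline visit [Day0] and seven follow-up visits [Day2, Day4, ..., Day14"], so post-baseline measurements are two days apart.

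SAP 7.2 asks for model-based group differences with "corresponding 95% confidence intervals" and adds: "Relevant timepoints will be Day 6 and Day14". It lists three pairwise contrasts: "The relevant blinded group comparisons are: A vs. B; A vs. C; B vs. C".

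The binary models contain, besides baseline status where applicable, "group allocation, sex, setting and time as fixed effects and random intercepts per ward and patients". The ordinal and linear models are "adjusted for baseline status, group allocation, sex, setting and time as fixed effects"; the linear model's within-patient structure is "random intercept per ward and patient as random effects". For every outcome type a nonparametric longitudinal analysis may replace the mixed model, depending on the distribution of the data.

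SAP 7.2 lists no group-by-time term, random slope, serial correlation, visit-specific variance or robust standard error. The only interactions named are subgroup by intervention (SAP 7.3). The example results table for secondary outcomes (SAP 10.2, Table 3) has one line per contrast and no column for visit.

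**The concern.** There are two linked gaps.

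1. **The timepoints cannot be read off the model.** With time as a main effect only, the fitted group difference is the same at Day 6 and Day 14. The SAP does not say how the two differences are obtained.
2. **The obvious repair is not enough.** An analyst who adds group-by-time and leaves the rest unchanged assumes that visits 2 and 12 days apart correlate equally, and that residual variance after adjustment for Day 0 is constant. For skin measurements every second day, neighbouring visits usually agree more closely, and the Day 0 value predicts Day 2 better than Day 14. The model spreads an average variance over all visits and so understates it at Day 14.

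At stake is the precision reported for secondary outcomes at the end of treatment. The trial's stated product is effect sizes for planning a confirmatory trial, so an interval that is too narrow feeds directly into that planning.

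**Working it through.** **Inputs from the documents.** Seven post-baseline visits, Days 2 to 14 (SAP 4.2); Day 0 as covariate, ward and patient random intercepts, 95% intervals (SAP 7.2); 220 patients in 20 wards, 25 + 195 (SAP 3); loss allowance 1 - 60/70 = 14.3% (SAP 6).

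**Assumed.** The documents give no serial correlation. The outcome has variance 1 and correlation ρ between visits two days apart, falling as a power of the lag (first-order autoregressive), with ρ from 0.3 to 0.95.

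**Method (linear model, large sample, complete data).** Number the visits t = 1 to 7. After adjustment for Day 0, the covariance of visits s and t is ρ^|s-t| - ρ^(s+t), so the variance at visit t is 1 - ρ^(2t). The random-intercept model estimates

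- within-patient variance W = (7/6) × (average visit variance - variance of the seven-visit mean)
- patient variance B = variance of the seven-visit mean - W/7

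and the error rate is 2 × [1 - Φ(1.96 × √(model variance / true variance))].

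**Step 1: the nominal level.** If a random intercept is true (correlation 0.5 at every lag), each adjusted variance is 1 - 0.25 = 0.75 and each covariance 0.5 - 0.25 = 0.25. Then B = 0.25, W = 0.50 and B + W = 0.75. Model and truth agree, and the error is 5.0% for every contrast.

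**Step 2: ρ = 0.7 in full.** Adjusted variance is 0.510 at Day 2, 0.882 at Day 6 and 0.993 at Day 14. The average is 0.8637 and the variance of the seven-visit mean 0.4246. So W = (7/6) × (0.8637 - 0.4246) = 0.512 and B = 0.4246 - 0.512/7 = 0.351.

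- *Common group effect, as the SAP is written:* model B + W/7 = 0.425, truth 0.425; error 5.0%.
- *Day 14, categorical time:* model B + W = 0.864, truth 0.993; ratio 0.870, standard error 93% of its true value, error 6.8%.
- *Day 14, linear time:* visit weights are 1/7 + 6(day - 8)/112, with sum of squares 1/7 + 36/112 = 0.464. Model 0.351 + 0.512 × 0.464 = 0.589, truth 0.996; ratio 0.592, standard error 77% of its true value, error 13.2%.
- *Day 6:* categorical 0.864/0.882, error 5.2%; linear 0.443/0.407, error 4.1%.

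**Step 3: range of ρ (error, %).**

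| ρ | Common effect | Day 14, categorical | Day 14, linear | Day 6, categorical | Day 6, linear |
|---|---|---|---|---|---|
| 0.3 | 5.0 | 5.2 | 8.6 | 5.2 | 5.5 |
| 0.5 | 5.0 | 5.6 | 10.8 | 5.4 | 5.1 |
| 0.7 | 5.0 | 6.8 | 13.2 | 5.2 | 4.1 |
| 0.9 | 5.0 | 10.4 | 16.8 | 3.7 | 2.6 |
| 0.95 | 5.0 | 12.0 | 18.0 | 3.1 | 2.3 |

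Adding a constant patient effect gives 8.4-17.4% (linear) and 5.4-11.3% (categorical) at Day 14. Adding measurement noise gives 8.1-12.1% and 5.6-7.6%. Random slopes instead of serial correlation give 6.5-14.0% and 5.9-11.1%.

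**Step 4: simulation with the trial's structure.** REML fits used the 220 patients, the 20 documented ward sizes and 14% dropout, with 800 runs per setting (Monte Carlo standard error about 0.8 points). With a true random intercept, errors were 5.6-5.9%. With serial correlation or random slopes, the common effect had 4.4-6.8%, Day 14 with linear time 8.5-20.5%, and Day 14 with categorical time 6.1-14.0%.

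**Step 5: the remedy.** A separate simulation of 4,000 null trials per setting, 73 patients per arm, gave 5.5-5.7% for a visit-specific baseline-adjusted analysis at Day 14. An unstructured covariance reproduces that analysis with complete data. The unstructured model itself was not fitted.

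**Binary and ordinal models.** A logistic random-intercept simulation (600 trials per setting, serial correlation, linear time) gave about 10% at Day 14 and about 5% for the common effect. This was not independently checked. The ordinal model was not simulated.

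**The case against.** The strongest reply is that SAP 7.2 does not specify the contrast that fails. It lists no group-by-time term, the example table has no visit column, and the one group effect the model delivers has a correct interval. Day 6 and Day 14 could also be served by descriptive statistics per timepoint or by visit-specific models, neither of which has the defect. This stands, and it makes the covariance problem conditional. It does not close the gap: SAP 7.2 asks for model-based differences, names two timepoints, and does not say how to get from one to the other.

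A reader might infer that all intervals from SAP 7.2 are too narrow, by a fixed amount, for every outcome. The documents do not support this. The effect in the written models keeps its level, Day 6 is not too narrow, and the size depends on correlations nobody has stated. With categorical time and ρ = 0.5 the error is only 5.6% in large samples and about 6.5% in simulation. Constant residual variance is a linear-model assumption; logistic and cumulative-link models have no free residual variance.

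The nonparametric alternative does not rest on the random intercept, but it is triggered by the distribution of the outcome, not by its correlation over time. Well-behaved data would stay with the mixed model.

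The trial is exploratory, without confirmatory tests. That limits the consequence to over-precise planning estimates; it does not make a mis-stated interval harmless.

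**Conclusion.** The point holds in conditional form and should be addressed.

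- **Certain from the text:** the written models give one group difference common to all visits and cannot give separate Day 6 and Day 14 differences.
- **Conditional:** if group-by-time is added and only random intercepts are kept, the linear model's Day 14 interval has about 5-12% error with categorical time and 8-18% with linear time, for ρ between 0.3 and 0.95. Simulation with dropout and wards reaches 14.0% and 20.5%. Day 6 lies between about 2.3% and 5.5%.
- **Scope:** the evidence is firmest for Mexameter erythema, measured in all patients at every visit. It is weaker for patient satisfaction (MMSE 24 or higher only) and NRS pain (also only with IAD present), and the size is uncertain for binary and ordinal outcomes.
- **Not affected:** IAD incidence, the main outcome, which is analysed by Cox regression.

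**What to change.** In SAP 7.2, state how the Day 6 and Day 14 differences are obtained, and give each outcome type a suitable covariance:

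- **Mexameter erythema:** visit as a category, group-by-visit and baseline-by-visit terms, unstructured within-patient residual covariance in place of the patient intercept, and the ward random intercept retained. Fallback if it does not converge: first-order autoregressive with visit-specific variances. Report both contrasts from this model.
- **Patient satisfaction and NRS pain:** the autoregressive structure from the start, or robust patient-level standard errors, because the subsets may be too small for an unstructured matrix.
- **Binary and ordinal outcomes:** add the group-by-time term and take intervals for the two contrasts from a patient-level bootstrap or robust standard errors.
- **SAP 10.2, Table 3:** add a visit column.

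The cost is SAP wording and model code; no new data are needed. The downside is more variance parameters (7 × 8/2 = 28 for seven visits) and possible non-convergence, which the named fallback covers.
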